- J. Describe the Research Questions or Hypotheses (that is, what questions are you trying to address by conducting the research.) The effectiveness of the V-WHI approach will be tested in the context of a randomized controlled trial (RCT). The following hypothesis will be tested: veterans receiving V-WHI will have better work outcomes at time 1 (T1) than the usual care group (BHL only) as measured by at-work productivity loss known as presenteeism. A sub-hypothesis for Aim 1 is that the V-WHI effect at T1 will be sustained at least until the final follow-up (T2). Secondary T1 outcome measures expected to improve include absenteeism, depression symptoms and health-related quality of life (HRQOL). Hypothesis 2 is that the return on investment (ROI in the V-WHI at time T1 will be positive, exceeding 1). Analysis of ROI will be contingent upon confirmation of Hypothesis 1. ROI will be estimated based on the marginal group difference in productivity (presenteeism and absenteeism combined) relative to the marginal V-WHI program costs.
- K. Primary Outcome Variable(s): (Define the primary outcome variable(s) used to support the study objectives (e.g. if the objective is to show that treatment A is superior to treatment B in the treatment of subjects with essential hypertension, the primary outcome variable is blood pressure measurement.) The main variables for outcomes analysis quantify health-related decrements in work performance and productivity (presenteeism). In addition, we will assess work loss and work retention based on employment status and other work outcomes such as weekly hours. To help us interpret the scores, we have extensive comparative data from clinic and population-based samples for the Work Limitations Questionnaire (WLQ), the WLQ Time Loss Absence Module,(11;12) and other employment status items (e.g., job loss).

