**Power Analysis and Sample Size** 

In this study, we wish to power the study to obtain an effect size that represents a minimally clinically important difference on the health outcomes and an economically important difference related to work productivity impact (the primary endpoint). Currently, MCID is established for the PHQ-9(2) and the PCS and MCS for the VR-12.

For the PHQ-9, we anticipate that the average subject will have an average baseline score of 15 on a 0-27 scale. A clinically-meaningful reduction of 5 points, which is stated in the literature, would have 100% power to be detected. For PCS and MCS, a clinically-meaningful 5-point improvement would afford 99% power.

With regard to Hypothesis 2, corresponding to the study's power to detect an economically important difference, the primary criterion is whether an ROI greater than 1 can be obtained. This analysis is described in the following section.

For presenteeism, a reduction of 1.2% in productivity loss (or a relative improvement of 1.2%) would have comparable value to the maximum expected cost of treatment, meaning that the economic value of treatment would exceed the cost. A sample size of 100 treatment and 100 controls after subject dropout would achieve an 83% power for this outcome. To be sure of getting these numbers based on previous success rates, we will recruit 250 subjects prior to 50-50 randomization within full time and part time strata.

4.2. Define plans for data and statistical analysis, including key elements of the statistical plan, stopping rules and endpoints.

In this section, we describe the methods for testing hypothesis 1, several additional analyses including testing related to the secondary study outcomes and sensitivity testing related to both the primary and secondary study endpoints and statistical power calculations. Following this section, there is a description of the methods for testing hypothesis 2, which consists of the ROI analysis.

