## PL1 = b\*PL0 + g\*X + c\*I(V-WHI) + error

where PL0 refers to the baseline WLQ productivity loss and PL1 refers to the post-treatment WLQ productivity loss, X represents a set of covariates such as full-time or part-time stratum assignment, age, gender, baseline depressive symptom severity and, prior depression, and, g represents their regression coefficients, and I(V-WHI) indicates that the veteran is assigned the experimental treatment. The regression coefficient c will be tested by a t-test at 5% significance level of c=0 vs. the alternative c $\Box$ 0. Although we believe that c<0 (the treatment reduces presenteeism) we test against inequality because a two-sided test is conservative and conventional.

The primary analysis is "intent to treat" that is, all persons assigned to each group will be followed up to the maximum possible extent, even if they drop out of IC or V-WHI treatment, and analyzed as a part of their assignment group.

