A third sensitivity issue is related to the relationship of T1 and T2 outcomes and ways they might be characterized. For these purposes, we would analyze T2-T1 outcomes to state how well the results were maintained, or analyze all measurements jointly using mixed models where there are random effects due to subject, e.g.,

PLit= g\*X + g1\*X\*T1 + g2\*X\*T2 + a1\*T1 + a2\*T2 + c1\*T1\* I(V-WHI) + c2\*T2\* I(V-WHI) + ei + eit

where the subscript t refers to the time, 0, 1 or 2, and T1 and T2 are indicator variables corresponding to T1 and T2.

Hypothesis 2. Cost Benefit Analysis/ROI Determination.

We will analyze the ROI of the experimental program if Hypothesis 1 is confirmed and test whether, consistent with Hypothesis 2, the ROI to achieve productivity gain is greater than 1. The general approach will be to compute the cost and benefit components of the ROI. The ROI is computed as the incremental cost minus the incremental monetized benefit divided by incremental cost (amount invested in the new program). A ratio exceeding one indicates a favorable ROI. Our Hypothesis 2 analysis will consider only that portion of the intervention's incremental cost related to the V-WHI and will quantify incremental benefit as the monetized value of productivity improvements. We will not consider consumption of resources not directly related to depression because of the complexity and scope of that type of analysis in this population. Nor will we include subject costs and benefits. Subjects presumably engage in the intervention because the resulting additional functional effectiveness and well-being outweigh their incurred costs (e.g., the time consumed). While we could measure the costs incurred by veterans in the program, we cannot measure the corresponding functional benefits in their personal lives.

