Benefits: We will compute benefits by quantifying and monetizing two components of productivity loss: presenteeism and absenteeism. For each component, we will compare the average change in the usual care and V-WHI care groups. We estimate productivity losses due to presenteeism using a validated WLQ Productivity Loss algorithm. Absenteeism is computed as hours of missed work during the time period divided by hours usually worked during that time period. Each productivity loss component will be monetized by multiplying it by the sample's median (fully loaded) wage. We use the median wage because we expect the wage distribution to be right skewed, making the mean less representative of the typical worker.

The benefit (i.e., reduced productivity loss) for the V-WHI intervention can be computed as follows. Let  $\triangle AP$  be the reduction in the proportion of time absent for V-WHI compared to usual care, while  $\triangle PP$  is the corresponding reduction in productivity loss due to presenteeism (i.e., the reduction in the proportion of output lost to presenteeism while working). Let H be the number of work hours during the period, while W is the median fully loaded wage rate. Then saved hours of productive output for V-WHI is H x ( $\triangle AP+\Delta PP$ ). Multiplying this result by W yields the monetized value of the reduced productivity loss.

Costs: The intervention's incremental cost has three components: 1) The value of time counselors spend in training is the product of their (fully loaded) wage rate and the number of hours needed to complete training; 2) The incremental value of time counselors spend counseling is the product of their fully loaded wage rate and the additional hours they spend counseling (compared to usual care); 3) The incremental value of time patients spend being counseled is the product of their fully loaded wage rate (the median veteran wage) and the additional hours they spend in counseling (compared to usual care).

The most straightforward cost and benefit analysis would compare the value of the benefit (i.e., the value of the reduced productivity loss) to the incremental cost of counseling. Because of the project's scale, changes in benefits will then be compared with changes in incremental costs.

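### Hypothesis 2 sets a cut-off of 1 for the ROI but gives no standard error, interval or test; read as benefit/cost, a break-even program is called favorable about half the time before the Hypothesis 1 condition

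*Combined protocol and SAP*

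**What the plan says.** Section J and the Hypothesis 2 text in section W.4.2 make an ROI above 1 a hypothesis to be tested, conditional on Hypothesis 1. The Power Analysis section (W.4.1) names the same threshold as the main criterion and refers the reader to the following section for the analysis.

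That analysis states the rule as "A ratio exceeding one indicates a favorable ROI". It writes ROI as incremental cost minus incremental monetized benefit, divided by incremental cost. The Benefits paragraphs take the group difference in average change for presenteeism and absenteeism, add the two, and multiply by work hours and the median loaded wage. The Costs paragraphs list counselor training, counselor time and patient time, and close with "The most straightforward cost and benefit analysis would compare the value of the benefit" against the incremental cost of counseling. None of these paragraphs attaches a measure of sampling error to the ratio.

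Hypothesis 1 is fully specified by comparison: "The regression coefficient c will be tested by a t-test at 5% significance level", and "we test against inequality because a two-sided test is conservative and conventional".

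**The concern.** Aim 2 is the economic claim that would support adopting the program. A hypothesis that is to be tested needs a decision rule with a known error rate, and the only one supplied is a cut-off on an estimate. If an analyst applies it literally, a ratio just above 1 counts as confirmation even when its interval includes large net losses.

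Precision is a practical problem here because the benefit includes absenteeism. The Secondary Analyses section describes absenteeism loss as strongly right-skewed, centered near 10% with some values toward 100%. It plans transformations for that outcome, but the ROI benefit is built from averages. Break-even is only 1.2 points of productivity loss.

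**Working it through.** **Inputs from the documents.** Break-even effect: "a reduction of 1.2% in productivity loss (or a relative improvement of 1.2%) would have comparable value to the maximum expected cost of treatment". Power: "A sample size of 100 treatment and 100 controls after subject dropout would achieve an 83% power for this outcome". Hypothesis 1 is two-sided at 5%. Randomized: 250 at CMCVAMC and 100 at VA TVHS, 1:1. Attrition at T1 is 10%, stated for CMCVAMC and applied here to both sites.

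**Not in the documents.** The presenteeism SD, the absenteeism SD and their correlation. The presenteeism SD can be back-solved. The absenteeism SD (10 to 20 points) and correlation (0.2) are assumptions.

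**Step 1: the plan's power figure.** Without an SD, 83% can only be inverted, not reproduced:

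SD = 1.2 / [(1.960 + 0.954) × √(2/100)] = 2.91 points (2.90 with the noncentral t), so SE = 2.90 × √(2/100) = 0.41.

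**Step 2: which ratio.** Take a program exactly at break-even.
- As written, (cost − benefit)/cost is 0, and it exceeds 1 only if the benefit is negative.
- With the sign reversed, (benefit − cost)/cost is 0, and it exceeds 1 only if the benefit is more than twice the cost.
- Benefit/cost is 1. Only this form matches the threshold and the 1.2-point break-even, so it is used below.

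**Step 3: presenteeism noise only, 100 per arm.** P(favorable) = 1 − Φ[(1.2 − δ)/0.41], where δ is the true effect.
- Break-even, δ = 1.2: 50%.
- Half of cost, δ = 0.6: 1 − Φ(1.46) = 7%.

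Hypothesis 1 needs an estimate above 1.96 × 0.41 = 0.80, so any estimate above 1.2 has already met it and these rates do not change.

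**Step 4: adding absenteeism.** With s the absenteeism SD and n per arm,

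SE = √(2/n) × √(2.90² + s² + 2 × 0.2 × 2.90 × s).

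The larger n is 350 × 0.90 / 2 ≈ 157. The 95% half-width for ROI is 1.96 × SE / 1.2. The true benefit is placed wholly in presenteeism. The last column is by Monte Carlo (normal estimates, fixed cost).

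| n per arm | s | SE | 95% half-width | Favorable, ignoring Hypothesis 1: half of cost vs break-even | Passes Hypothesis 1 and favorable: half of cost vs break-even |
|---|---|---|---|---|---|
| 100 | 10 | 1.55 | 2.5 | 35% vs 50% | 17% vs 46% |
| 100 | 20 | 2.94 | 4.8 | 42% vs 50% | 18% vs 45% |
| 157 | 10 | 1.24 | 2.0 | 31% vs 50% | 21% vs 49% |
| 157 | 20 | 2.35 | 3.8 | 40% vs 50% | 23% vs 49% |

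**Step 5: requiring the lower 95% limit of benefit to exceed cost.** P = 1 − Φ[1.96 − (δ − 1.2)/SE].
- Break-even: 2.5% for any SE, before the Hypothesis 1 condition. At half of cost it is lower still.
- Benefit twice cost (δ = 2.4), presenteeism noise only: 83%.
- Benefit twice cost, 100 per arm, uncorrelated absenteeism with s = 10 (SE 1.47): 13%. With s = 20 (SE 2.86): 6%.

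**The case against.** The plan says it will test the hypothesis, and its power section speaks of power to detect an economically important difference. Nowhere does it say that sampling error will be ignored, so a decision on the point estimate alone is inferred from a missing method. The Secondary Analyses section also commits to ANCOVA tests of combined presenteeism and absenteeism loss, the quantity that drives the benefit. This is fair as to intent, but it does not fill the gap. Those tests compare the effect with zero, not with cost, and neither they nor the transformations are carried into the ROI.

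A reader might infer something stronger: that a program worth half its cost would be called favorable almost as often as one at break-even, so that the result hardly depends on the true ROI. The documents do not support this. On the SE implied by the plan's own power, the rates are 7% and 50%. Over the whole procedure, including the Hypothesis 1 condition, they differ two- to threefold even with the assumed absenteeism noise. They come close (46% to 57% in both cases) only among trials that have already passed Hypothesis 1, and only with an absenteeism SD that the documents do not give.

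It would also be wrong to say that the plan as written passes a break-even program half the time. The 50% belongs to benefit/cost. Under the sign-reversed net form it would be about 0.2% on presenteeism noise alone, because the benefit estimate must then exceed 2.4 points.

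**Conclusion.** The point holds in limited form. Hypothesis 2 has a threshold but no standard error, interval or test, and its written formula does not match the threshold. Read as benefit/cost, the rule calls a break-even program favorable about 50% of the time before the Hypothesis 1 condition. For a program worth half its cost, the rate is about 7% on presenteeism noise alone. With the assumed absenteeism SD and correlation it is about 31-42% before the condition and 17-23% after it, against 45-49% after it at break-even.

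The 50% needs only benefit/cost and an estimate whose median is the true value. The 7% rests on the back-solved SD. The remaining rates rest on the assumed absenteeism figures, normal estimates, fixed cost, hours and wage, and a benefit lying wholly in presenteeism. Skewed data, uncertain costs, or a benefit that falls partly in absenteeism would change them.

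This should be fixed before the ROI is analyzed. It is not critical, because Aim 2 is contingent and the primary hypothesis is unaffected.

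**What to change.** In the Hypothesis 2 text, define the criterion as benefit/cost above 1, or equivalently net benefit (benefit minus cost) above zero, and correct the written formula to agree with it.

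Then add the inference. Resample veterans within arm and full/part-time stratum, recomputing the presenteeism and absenteeism effects, the median wage and the per-veteran cost in each resample. Report the ROI with its 95% interval. Call Hypothesis 2 supported only if the lower limit of the two-sided 95% interval for net benefit is above zero; otherwise report it as inconclusive. Basing the decision on net benefit avoids the instability of a ratio.

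The work is one paragraph and a short bootstrap program on data already being collected. The real cost is fewer positive findings. Even at a true benefit of twice cost, the chance of success is about 83% if only presenteeism noise matters, but perhaps 6-13% if the absenteeism SD is 10-20 points (assumed, uncorrelated, 100 per arm). The team should state this when adopting the rule, since it reflects how precisely a trial of this size can estimate the ROI.

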To assist the study in determining the degree to which measured changes in WLQ and/or PHQ-9 scores are perceptible to the veteran we will have the VR-12 PCS and MCS scores. In a treatment study in which a new type of care is being evaluated, it is useful to measure the consumers' experience of care. It is important to know whether the veterans found the care to be of a high quality, a reasonable cost (in terms of personal time and effort), effective and satisfactory. To assist us in obtaining this information, we will use a modified version of the CAHPS survey for behavioral health programs (74). One of the issues we will probe specifically is veterans' preference for different types of interventions. For instance, we can evaluate perceptions of key parts of the V-WHI such as the CBT workbook and the homework assignments. We can also probe to find out if veterans would be interested in an employer outreach component. This information can be helpful to future versions of the program.

We will also collect a range of other variables which will facilitate analysis of the baseline comparability of the treatment groups, the impact of any differential attrition that may occur (such as the need for adjustments in the outcomes analysis), and supply rich descriptive data about veterans with depression, their work and their care. The study will assess: veteran demographics; military history; work history; current job demands autonomy and supports at work; job earnings; physical and mental health; current and past treatment for mental health and/or behavioral health problems; utilization of VA, workplace and community support services (e.g., EAPs and vocational training); and current and past disability claims and decisions.(75)

Finally, to support the economic analysis, utilization and cost data will be collected from questions on the study's self-report surveys, the electronic health records maintained by the VHA for each veteran, and, for the experimental treatment group, the V-WHI counselor data system. The costs of delivering the V-WHI will be determined mainly on the basis of counselor and clinical supervision hours, which are mostly captured by the study's counselor website.

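### The ROI analysis both excludes and charges veterans' counseling time, so Hypothesis 2 has two cost denominators and the verdict can depend on which is used

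*Combined protocol and SAP*

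**What the plan says.** Section W.4.2, under Hypothesis 2 (Cost Benefit Analysis/ROI Determination), limits the analysis to V-WHI cost and monetized productivity. On participants it says: "Nor will we include subject costs and benefits". The reason given is that veterans presumably take part because their gains "outweigh their incurred costs (e.g., the time consumed"), and that gains in personal life cannot be measured even though the costs could be.

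The Costs paragraph that follows says incremental cost has three components: counselor training time, counselor counseling time, and "3) The incremental value of time patients spend being counseled is the product of their fully loaded wage rate", using the median veteran wage, multiplied by the hours beyond usual care.

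Four other statements bear on the same calculation:

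- **Formula (W.4.2):** "The ROI is computed as the incremental cost minus the incremental monetized benefit divided by incremental cost", with a value above 1 counted as favourable.
- **Benefit (W.4.2):** work hours × (reduction in absence + reduction in presenteeism loss) × median wage. The hours are introduced only as "Let H be the number of work hours during the period".
- **Break-even (W.4.1, Power Analysis and Sample Size):** a 1.2% reduction in productivity loss "would have comparable value to the maximum expected cost of treatment", "meaning that the economic value of treatment would exceed the cost".
- **Data collection (O.2.1.2):** "The costs of delivering the V-WHI will be determined mainly on the basis of counselor and clinical supervision hours, which are mostly captured" by the counselor website. The project timetable text (O.2.2) plans weekly supervision.

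**The concern.** The same item is removed from the ROI in one paragraph and charged in the next. Reading subject costs as out-of-pocket expenses does not help, because time is the example the exclusion gives. No rule says which paragraph prevails.

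Hypothesis 2 compares a ratio with a fixed threshold, and the ROI is run only if Hypothesis 1 is confirmed, so the presenteeism benefit will already be known. If the cost list is still open then, it can be chosen with the answer in view. The formula and the undefined period leave further room for choice.

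Supervision is a lesser mismatch. It is a main cost basis in O.2.1.2 but is not among the three components.

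**Working it through.** **The plan's own figure.** W.4.1 gives 83% power for a 1.2-point difference with 100 per arm. No SD is stated. At two-sided 5%, the implied SD is 1.2 / ((1.960 + 0.954) × √(2/100)) = 2.91 points. Recruiting 250 with 20% loss leaves 200. Neither figure depends on the cost list. The 1.2% break-even cannot be rebuilt, because no wage, program cost or number of work hours is given.

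**Inputs from the plan.** Eight 50-minute sessions over the initial four months (O.1.1, CBT component): s = 8 × 50/60 = 6.67 hours per veteran. The calls are one to one, so counselor session hours are the same. The minimum working week is 15 hours (R.2.1.1).

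**Assumptions.** Four months = 17.3 weeks. Veteran wage/counselor wage r is 0.5 to 1.0. All sessions are attended and additional to usual care. There is no training or supervision cost, and the benefit is presenteeism only.

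**Cost in veteran-wage hours.** Without veteran time, s/r. With it, s/r + s. The multiplier is 1 + r, or 1.5 to 2.0. Any training or supervision cost would lower it, so for a given r it is an upper bound.

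**Hours saved at 1.2%.** 0.012 × 15 × 17.3 = 3.1, and 0.012 × 40 × 17.3 = 8.3.

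**Benefit/cost at 1.2% = 0.012 × H / cost:**

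| H (hours) | r | Without veteran time | With veteran time | Against 1 |
|---|---|---|---|---|
| 519 (30 × 17.3) | 1.0 | 0.93 | 0.47 | both fail |
| 692 (40 × 17.3) | 1.0 | 1.25 | 0.62 | disagree |
| 692 | 0.5 | 0.62 | 0.42 | both fail |
| 2,080 (40 × 52) | 1.0 | 3.74 | 1.87 | both pass |

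**Where the lists disagree.** At 1.2% this needs H between (s/r)/0.012 and (s/r + s)/0.012: 556 to 1,111 hours at r = 1.0, and 1,111 to 1,667 at r = 0.5. For any effect, they disagree when benefit/cost without veteran time lies between 1 and 1 + r. At H = 692 that is a combined reduction in productivity loss of 6.67/692 = 0.96% to 13.33/692 = 1.93% at r = 1.0, or 13.33/692 = 1.93% to 20/692 = 2.89% at r = 0.5.

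**The formula.** (cost − benefit)/cost = 1 − benefit/cost, which is below 1 whenever the benefit is positive. If net return, (benefit − cost)/cost > 1, was meant, the criterion is benefit/cost > 2, and the lists disagree when the ratio without veteran time lies between 2 and 3 (r = 0.5) or 2 and 4 (r = 1.0). On that reading the 2,080-hour example also splits: 3.74 − 1 = 2.74 against 1.87 − 1 = 0.87.

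**Supervision.** One assumed hour per veteran at the counselor wage adds 1/6.67 = 15% to session cost, and half an hour adds 7.5%. At H = 692 and r = 1.0, one hour moves 1.25 to 8.30/7.67 = 1.08.

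**The case against.** The Costs paragraph is itemised and can be followed on its own. Both versions can be computed from the same data. Section J speaks of marginal program costs and Hypothesis 2 of the amount invested in the new program, which lean towards leaving veteran time out. All of that is fair, but none of it cancels the third component. The analyst still has two instructions that give two answers.

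The numerical criticism has more force. Section J ties the ROI to T1, at month 4 to 5, so H would run from about 260 hours (15 × 17.3 weeks) to 867 (40 × 21.7 weeks), and the 52-week example lies outside that. On that horizon, at exactly 1.2% and r = 0.5, both lists fail throughout. At r = 1.0 and 17.3 weeks, disagreement needs about 32 hours a week (556/17.3). The planned benefit also includes absenteeism, which the 1.2% examples omit. These points narrow the examples. They do not remove the problem, because the combined reductions that split the verdict at 40 hours a week run from 0.96% to 2.89% over the two wage ratios.

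It is also right that supervision is an omission between sections and not a contradiction. O.2.1.2 describes data sources and hedges, and the supervision hours used above are assumed.

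**Conclusion.** The concern holds. Veterans' counseling time is excluded and charged within one section, so the ROI has no single denominator, and the printed formula cannot meet its own criterion. Counting the time raises cost by up to 50% to 100% for wage ratios of 0.5 to 1.0. That reverses the Hypothesis 2 verdict for some plausible hours, wages and effects, and leaves it unchanged for others. H, wages, training hours and supervision hours are not in the documents, so these figures are illustrations. The textual conflict depends on none of them.

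The effect is confined to Aim 2. The primary test, its power and the randomization are untouched. The economic rationale for 1.2% is affected, because it rests on an unstated cost list and period. This should be fixed before analysis.

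**What to change.** 1. State one cost list, the same in the exclusion sentence and the Costs paragraph. The plan's reason for setting subject costs aside supports a base case without veteran time: counselor training, counselor session hours and, following O.2.1.2, clinical supervision. Veteran time then becomes a labelled sensitivity analysis. If the sponsor prefers to keep the third component, amend the exclusion sentence and report the ROI without it as the sensitivity analysis.
2. Replace the formula with one that fits the threshold. The break-even wording in W.4.1 fits benefit/cost > 1.
3. Define H, and say which cost list and period underlie the 1.2% break-even, or recompute it.
4. Name a source for training hours and for any supervision hours the counselor website does not capture.

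The cost is a change of wording in W.4.1 and W.4.2, one extra sensitivity run, and possibly another source for some hours. Including supervision makes the ratio somewhat less favourable.

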#### 2. Design

2.1. What research methods will be used in the project? Check all that apply.

| Surveys/Questionnaires  | Interviews    | Audio Taping                          |
|-------------------------|---------------|---------------------------------------|
| Behavioral Observations | Chart Reviews | Video Taping                          |
| Focus Groups            | Randomization | Double-Blind                          |
| Control Group           | Placebo       | Withhold/Delay Treatment              |
| Specimen Collection     | Deception     | Telephone Survey                      |
| Other (Describe)        |               | · · · · · · · · · · · · · · · · · · · |

2.2. Describe how randomization or other treatment assignment will be made. The RCT will involve random assignment of 250 consenting subjects at the Cpl.

Michael J. Crescenz VAMC, and 100 at the VA TVHS . For practical reasons,

neither subjects nor the intervention providers will be blinded to subject assignment. Subject assignment will be a 50/50 ratio to V-WHI care or BHL usual care (no V-WHI care). Participants are not required to engage in BHL clinical care. Both groups are permitted to use other services through their own VA or other insurance coverage or out-of-pocket expenditures. With attrition at our site, we expect 225 at initial follow-up (month 4 to 5) and 200 at final follow-up (month 9); attrition rates of 10% and, in total, 20%.

The randomization procedure will be automated within full/part-time group using a block randomization technique within group, where part-time is defined as less than 30 hours per week. Each block of 4 will contain 2 V-WHI and 2 BHL, randomly ordered. The small block sizes assure an even flow of new cases to the counselors.

- 2.3. For retrospective research studies, provide the "look-back" period. (e.g., December 1, 1999 through December 31, 2008.) N/A
- 3. **Study Duration** 
  - Provide the estimated length of time to enroll all subjects and complete the study. 44 3.1. months will complete subject data collection; 48 months will complete analysis, reporting, and dissemination.

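### The ROI benefit is described as a comparison of average change, without the baseline adjustment planned for the same outcomes elsewhere: a loss of precision and consistency, not a bias

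*Combined protocol and SAP*

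**What the plan says.** All references are to the statistical analysis section (W.4) of the combined protocol and SAP, unless another section is named.

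- **Hypothesis 1.** T1 productivity loss is regressed on baseline productivity loss, covariates and treatment: "where PL0 refers to the baseline WLQ productivity loss and PL1 refers to the post-treatment WLQ productivity loss". The effect is the treatment coefficient: "The regression coefficient c will be tested by a t-test at 5% significance level".
- **Aim 1, Secondary Analyses.** Absenteeism, and productivity loss from presenteeism and absenteeism combined, are to be analysed with similar ANCOVA models.
- **Hypothesis 2, ROI.** The ROI is analysed only if Hypothesis 1 is confirmed. For presenteeism and absenteeism, the benefit is obtained thus: "For each component, we will compare the average change in the usual care and V-WHI care groups". The presenteeism input, delta-PP, "is the corresponding reduction in productivity loss due to presenteeism". The absenteeism input, delta-AP, is likewise a reduction relative to usual care. The two are added, then multiplied by work hours and the median wage.
- **Research questions (section J).** The ROI input is called a marginal group difference, with no estimator named.

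Nowhere is delta-PP or delta-AP tied to an ANCOVA coefficient.

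**The concern.** The plan will already hold a baseline-adjusted estimate of each ROI component, but the ROI text describes another estimator for the same quantities. A difference in average change subtracts the whole of any chance baseline imbalance. ANCOVA subtracts only the share that the data show carries over to T1. When that share is below one, the change score over-corrects and is noisier.

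The ANCOVA decides whether the ROI is computed at all, and a different number is then turned into money. Because Aim 2 is judged against a threshold, a reader could be shown a presenteeism effect in the primary results and a visibly different one inside the ROI, with no pre-specified reason for the gap.

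**Working it through.** **1. The plan's own figure.** The Power Analysis section gives the effect ("For presenteeism, a reduction of 1.2% in productivity loss", read here as 1.2 points on the productivity-loss scale) and the power: "A sample size of 100 treatment and 100 controls after subject dropout would achieve an 83% power for this outcome". No SD is stated, so 83% cannot be reproduced independently; it can only be solved for the SD. At two-sided 5%, the standard error must be 1.2 / (1.960 + 0.954) = 0.412, so SD = 0.412 / sqrt(2/100) = 2.91 points. The plan does not say whether this is a raw, change or ANCOVA residual SD.

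**2. Variance of each estimator.** Let s0 and s1 be the baseline and T1 SDs and r their correlation. The per-patient variances are:

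- change score: s0² + s1² − 2·r·s0·s1
- ANCOVA: s1²·(1 − r²)
- change minus ANCOVA: (s0 − r·s1)², which is never negative (ignoring the cost of estimating one slope, negligible with about 225 patients).

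With s0 = s1 the ratio of change to ANCOVA is 2(1 − r)/(1 − r²) = 2/(1 + r). The correlation is not in the documents, so 0.3 to 0.7 is assumed. Eligibility requires a productivity loss of 5% or more, which may narrow the baseline spread, so s0/s1 = 0.85 is shown as well.

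| r | Ratio, equal SDs | Ratio, s0/s1 = 0.85 |
|---|---|---|
| 0.3 | 2/1.3 = 1.54 | 1.2125/0.91 = 1.33 |
| 0.5 | 2/1.5 = 1.33 | 0.8725/0.75 = 1.16 |
| 0.7 | 2/1.7 = 1.18 | 0.5325/0.51 = 1.04 |

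**3. How far apart the two presenteeism estimates fall in one trial.** They differ by (1 − b) times the chance baseline imbalance, where b is the ANCOVA slope (b = r for equal SDs). The SD of this difference is (1 − b)·s0·sqrt(2/n). The Design section expects 225 patients at T1 from the 250 randomised at the main site, with 1:1 allocation, so n = 112.5 per arm and sqrt(2/112.5) = 0.133. With b = 0.5:

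- 2.91 read as the raw SD: 0.5 × 2.91 × 0.133 = 0.19 points, and 0.19/1.2 = 16%
- 2.91 read as the ANCOVA residual SD: raw SD = 2.91/sqrt(0.75) = 3.36, so 0.5 × 3.36 × 0.133 = 0.22 points, and 0.22/1.2 = 19%.

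**4. Opposite sides of break-even, presenteeism alone.** A simulation of 40,000 trials per setting used 100 per arm, equal SDs and 2.91 as the residual SD. Among trials with a significant Hypothesis 1, the two estimates fell on opposite sides of 1.2 points in 24%, 20% and 15% (r = 0.3, 0.5, 0.7) when the true effect was 1.2. When it was 1.5, the figures were 17%, 14% and 11%. The simulated means of the two estimators agreed.

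**The case against.** The strongest reply is that the ROI text is silent on adjustment. It speaks of average change and never calls it unadjusted, and an ANCOVA coefficient is also a reduction relative to usual care. This stands in part: the investigators may have meant an adjusted difference. But the only operation described is a comparison of average changes, and nothing points to the ANCOVA. If adjustment was meant, the same wording change settles it.

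A reader might infer that the ROI would value a different effect from the one tested, or a biased one. The documents do not support that. Under randomisation, and leaving differential dropout aside, both methods estimate the same T1 group difference. Nor was absenteeism ever part of Hypothesis 1; there the inconsistency is with the secondary ANCOVA.

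A reader might also infer that the ROI verdict is likely to flip. That is not shown. The 24%, 20% and 15% place the true effect exactly at break-even, the worst case. The 1.2 points concern presenteeism only, whereas the ROI adds absenteeism, so 16 to 19% of 1.2 is not the error in the ROI.

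Finally, average change has one advantage: it leaves the analyst no choices. The Hypothesis 1 covariates are given only as examples, and the Sensitivity Testing section would add any baseline variable that differs at p<0.05. That objection stands, and it is why the covariates must be fixed in advance.

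**Conclusion.** The point holds as one of efficiency and consistency. As written, the ROI rests on an estimator whose variance is never smaller than that of the planned ANCOVA. The excess runs from 4% (correlation 0.7, narrower baseline spread) to 54% (correlation 0.3, equal SDs). The typical chance gap between the two presenteeism estimates, about 0.2 points, is modest but not trivial beside a 1.2-point break-even. These sizes rest on an assumed correlation and SD ratio, and on an SD recovered from the power statement. The direction of the comparison does not depend on them. Neither the trial nor the Hypothesis 1 test is affected.

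**What to change.** In the Benefits paragraph under Hypothesis 2:

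- Define delta-PP as minus the coefficient c from the T1 Hypothesis 1 ANCOVA, with its covariates fixed before the data are seen.
- Define delta-AP as minus the treatment coefficient from the matching T1 ANCOVA of the untransformed absence proportion, with baseline absence as a covariate. The secondary analyses plan transformations because absence is right-skewed; a transformed effect cannot be multiplied directly by hours and wage, so state this reason.
- Keep the unadjusted comparison of average change as a sensitivity analysis.

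Table 1 already schedules the WLQ and the Time Loss Module at baseline and T1, so no new data are needed. The cost is a little extra analysis and dependence on the pre-specified covariate set. A joint bootstrap of the two components, to give the ROI an interval, would be a useful but separate and optional addition.
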